4.4.1. Study discontinuation

N/A

4.4.2. Concomitant medication (if applicable)

N/A

4.5. Risks and Benefits**4.5.1. Risks**

Eligible participants will be approached only after IRB approvals have been obtained. After the study is thoroughly explained, they will be invited to participate. Those who consent to participating will be included. An HMMH-approved certified medical interpreter will be retained for the duration of the study to ensure information is delivered in a language-appropriate manner. The interpreter will receive four (4) hours of coaching prior to study initiation to enhance their understanding of study purpose and design.

To minimize the risk, albeit small, of breach of confidentiality, all hard copy data will be stored securely in a locked file cabinet in a private office at JFKUMC Plainfield Health Connections accessible only to the PI. Data will be stored on an HMH-issued, password-protected laptop accessible only to the PI, following which all hard copies will be destroyed. All participant data will be assigned a unique study ID that will be linked to their data throughout the study.

Participation in the survey and educational intervention is voluntary. Potential risks include breach of confidentiality and risk of disclosure of responses. The surveys will be coded. In any future published report based on findings from this study, the PI will ensure no information is included that could make it possible to identify individual participants. Other risks include potential discomfort with survey questions. Participants may skip any questions they do not feel comfortable answering.

4.5.2. Benefits

As a result of participation in this five-week C-DSME program, participants may gain increased knowledge, which can potentially lead to better self-management practices and subsequently, improved glycemic levels and overall clinical outcomes. Participation may also generate knowledge that can help determine the potential benefits of community-based C-DSME programs to adult Hispanic males living with T2DM.

Each participant will receive a \$25 Visa card to offset the cost of transportation to the in-person sessions after participation in all 5 sessions.

5 – Methods

5.1. Screening

Only participants who meet elements of the inclusion criteria will be contacted for study participation.

5.2. Recruitment, Enrollment and Retention

Recruitment flyers (Appendix A) will be posted and distributed in high visibility areas at the JFKUMC Family Medicine and Diabetes Centers, through the Plainfield Health Connections program, and a community-based family practice located in Plainfield. Recruitment will also occur via community settings where members of the Hispanic/Latinx study population are largely represented. Physical settings may include places of worship, community centers, local community organizations, hospital and community based ambulatory care settings. Using convenience sampling strategies, the PI will contact eligible participants who express interest and are willing to participate, either in person or via telephone, with the assistance of the interpreter, and invite them to participate. Interested participants will also be able to contact the PI whose information will be shared through the recruitment flyer. Upon agreement to participate, consent will be obtained electronically through REDCap or via a

paper and pencil copy where applicable. Efforts will be made to ensure participants know in advance that attending the educational program requires participation in the study.

5.3. Study Intervention (including schedule of events and study visits)

The PI, a board-certified adult nurse practitioner with more than 10 years of experience in health education and providing care to persons with T2DM, will be implementing the C-DSME intervention in this study, accompanied by a certified Spanish medical interpreter. This educational intervention will be delivered in group sessions for five (5) consecutive weeks using a hybrid format (via Google Meet) and at the HMH JFKUMC School of Nursing classroom across from the Plainfield Health Connections office with each session lasting approximately two (2) hours (for a total of 10 hours over the five week period).

The Spanish version of the Summary of Diabetes Self-Care Activities survey (Appendix B) will be completed by each participant electronically (via REDCap) or via paper and pencil (with assistance from the PI and interpreter as needed) at the beginning of Week 1 (pre-intervention) and again at the end of Week 5 (post-intervention) for comparison.

This C-DSME intervention will be modeled after the ADCES7 Framework, derived from national standards and consistent with current, evidence-based clinical practice guidelines for T2DM education in adults (ADA, 2022; ADCES, 2021; Powers et al., 2021). The main focus will be on three of the seven ADCES7 self-care behaviors, namely, (a) Healthy Eating, (b) Staying Active, and (c) Medication Use (ADCES, 2021).

Pertinent bilingual educational materials downloaded from the ADA and ADCES websites will be distributed to participants during weekly sessions. The C-DSME intervention will cover the following components and will be structured as follows:

- **Weeks 1–2:** A brief overview of T2DM will be provided, followed by discussions on healthy coping, cultural beliefs about food; healthy eating, including MyPlate method of meal planning for persons with T2DM; incorporation of fruits and vegetables in daily meals; consumption of whole grains, lean meats and plant-based proteins; healthy fats and oils; healthy snacks and beverages.
 - Healthy snacks and water will be provided during classes.
 - Participants will receive culturally friendly recipes to try at home.
 - A compilation of local grocery stores carrying affordable, healthy foods will be distributed.
 - Sessions will be interactive and engaging, and will involve the use of visual aids, pictographs, and teaching aids to enhance learning.
- **Week 3:** Discussion will focus on physical activity and exercise; participants' beliefs and values regarding exercise will be explored; benefits of exercise will be discussed,

and each participant will be encouraged to commit to a weekly exercise regimen in accordance with ADA and AHA guidelines.

- **Week 4:** Participants' beliefs and values regarding medication use will be explored. Topics to be covered will include rationale for medication use; indications; dosage; frequency; adherence; herbs and supplement use; among others.
- **Week 5:** This interactive class will include discussions on effective self-monitoring, risk reduction, and problem solving. Further, participants will be given a chance to ask questions, provide feedback, and interact with each other. Participants will be invited to share what they have learned and how it can be applied to enhance their daily self-care practices and behaviors.

Methodological Rigor

For the proposed study, steps taken by the PI to enhance rigor are as follows:

- Prior to formulating the hypotheses, the PI thoroughly engaged with the current empirical and theoretical evidence related to DSME and T2DM. This was necessary to ensure congruency between hypotheses, literature review, and proposed methodology (Goodman et al., 2020).
- The existing body of evidence on DSME and T2DM was critically appraised and synthesized; the gap that emerged following this critical appraisal, which led to the proposed research study, was clearly identified (Goodman et al., 2020).
- *A priori* power analysis was completed to guide sample size determination (Cohen, 1992). This was done to control for the potential threat to statistical conclusion validity that can occur due to low statistical power, often associated with inadequate sample size selection (Gray et al., 2017).
- The Spanish version of the Summary of Diabetes Self-Care Activities (SDSCA-Sp) survey, the instrument of measure proposed for this study, is reliable and valid (Vincent et al, 2008), which can enhance statistical conclusion validity.
- The nonrandomized, one-group, pretest-posttest quasi-experimental design lacks a control group and randomization, which can pose a threat to internal validity of the study (Goodman et al., 2020). The pretest-posttest feature, which allows the sample to be their own control, can minimize this potential threat. Additionally, the proposed intervention will be implemented in a systematic and uniform manner, to further control for this threat (Flannelly et al., 2018).

- The proposed target population, setting, inclusion/exclusion criteria for sample selection, are clearly outlined for this research proposal. According to Goodman et al. (2020), clear presentation of information can potentially minimize threats to external validity.
- **Virtual Sessions**
 - Sessions will not be recorded
 - Participants may turn their cameras off if they choose (this will be announced at the beginning of each virtual session)
 - Participants may use an alternate pseudonym rather than their given name for privacy
 - Virtual link (via Google Meet) will be shared via text using Twilio messaging through REDCap along with weekly reminders

5.4. Assignment / Randomization (if applicable)

Convenience sampling will be used.

5.5. Section on Instruments (to include for all studies with a social behavioral intervention)

The SDSCA-Sp survey (Vincent et al., 2008) will be used as the instrument of measure in this study. The SDSCA, originally developed by Toobert et al. (2000), was selected for the proposed study because it has been established as a psychometrically sound instrument proven effective for assessing DSM behaviors in adults with T2DM in many settings across the globe for more than 20 years (Dietz et al., 2022; Gehlawat et al., 2019; Hailu et al., 2019; Zheng et al., 2019). Additionally, it is congruent with the purpose and desired outcomes of the proposed dissertation study.

The SDSCA is a brief, 11-item self-report questionnaire used to measure levels of self-management across different components of the DM regimen (Toobert et al., 2000). It is designated for use in research and practice in a variety of settings, including outpatient clinics and wellness centers, in-person or via the internet. It can be completed in paper and pencil or electronic formats, and in one-on-one or group-based scenarios (Toobert et al., 2000).

The SDSCA is recommended for use in clinical practice and research to assess DSM, which includes blood glucose self-monitoring, healthy eating, keeping active, and foot care, among others (Powers et al., 2021). Core aspects of DSM the SDSCA focuses on are general diet, exercise, blood glucose monitoring, foot care, and smoking (Toobert et al., 2000).

The SDSCA is a Likert-type instrument with five subscales (diet, exercise, blood glucose monitoring, foot care, and smoking) consisting of 11 core items and 14 extra items, all of

which are believed to have value in clinical practice and research. For ease of scoring and interpretation, all items on the scale are consistently scored using the metric “days per week” (Toobert et al., 2000).

The 11 core items measure participants’ DM self-care activities during the past seven days. In case of sickness during that period, participants are asked to respond based on the last seven days they were not sick (Toobert et al., 2000). Items 1–4 relate to dietary behaviors, for example, “how many of the last seven days have you followed a healthful eating plan?” Items 5–6 pertain to exercise activity, for example, “on how many of the last seven days did you participate in at least 30 minutes of physical activity?” Items 7–8 apply to blood sugar testing, for example, “on how many of the last seven days did you test your blood sugar?” Items 9–10 correspond to foot care activities, for example, “how many of the last seven days did you check your feet?” Item 11 focuses on smoking habits, for example, “have you smoked a cigarette in the past seven days?”

Scores are calculated separately for each of the five subscales. For items 1–10, number of days per week an activity is performed, on a 0–7 scale, is recorded, with higher numbers corresponding to higher levels of self-care activity performance (Toobert et al., 2000).

General diet is scored using the mean number of days for core items 1 and 2. Specific diet is scored using the mean number of days for items 3 and 4, reversing item 4 (recommendation is to use individual items due to low inter-item correlations for this scale). Exercise is scored using the mean number of days for items 5 and 6. Blood glucose testing is scored using the mean number of days for items 7 and 8. Foot care is scored using the mean number of days for items 9 and 10. Smoking status is scored using item 11 (0 = non-smoker; 1 = smoker) and number of cigarettes smoked per day (Toobert et al., 2000).

The additional 14 items constitute the expanded version of the SDSCA and are used when a particular question is of interest for clinical or research purposes (Toobert et al., 2000). Of note, there is little to no reliability or validity data for the additional items of the SDSCA. Six of the items address self-care recommendations and may help clarify patient understanding of self-management. For example, “which of the following medications for your diabetes has your doctor prescribed” specifically addresses medication use. In terms of scoring, none is required for items 1A–4A, and 12A–14A. Item 5A provides additional information on diet and is scored as the total number of days per week. Item 6A (total number of days per week), or items 7A and 8A (mean number of days per week) provide scores for medication use. Mean number of days per week for items 9A–11A, after reversing 10A and including items 9 and 10 from the brief version, provides scores on foot care (Toobert et al., 2000).

To complete the SDSCA, respondents are asked to circle how many days in the last seven days they performed a specific behavior pertaining to each of the subscales (Toobert et al., 2000). Response choices range from zero to seven, with higher scores indicating higher self-care activity performance.

The SDSCA-Sp has been established as easy to read at a sixth-grade readability level (Vincent et al., 2008). It has been previously used successfully in a study involving Mexican American adults with T2DM (Vincent et al., 2008). Regarding content validity, it is reported as being “exactly equivalent” to the original English version by Toobert et al. (2000) following expert translation and back translation. Additionally, the authors have noted that the SDSCA-Sp has high test-retest reliability ($M = .84$) and moderate internal consistency ([Cronbach’s alpha, $\alpha = 0.72$]; Vincent et al., 2008), both of which speak to the quality of the instrument.

Pertinent demographic data that will be used to describe the sample (age, race/ethnicity, marital status, preferred language, health insurance status, educational level, and employment status) will be collected on each participant using a demographic form (Appendix C) during the first session. Demographic data and completed SDSCA-Sp questionnaires will be uploaded into an HMH-issued laptop computer for secure storage via an encrypted password known only to the PI. Once the information is uploaded, all paper forms will be destroyed to maintain confidentiality. Permission has been obtained to use surveys pertinent to this study.

5.6. Follow-up and end-of study (if applicable)

5.7. Statistical Method

5.7.1. Sample size calculation and justification

A priori power analysis was completed to guide sample size determination (Cohen, 1992). This was done to control for the potential threat to statistical conclusion validity that can occur due to low statistical power, often associated with inadequate sample size selection (Gray et al., 2017).

Based on published SDSCA data for diet and a calculated effect size of 0.41 (doi:10.1177/0145721712443292), an alpha of 0.05 and power of 0.80 for a paired two-sided test, a sample size of 49 is adequate. Assuming a 50% incompleteness rate, a sample size of 98 would be able to detect a pre- and post-survey difference at 80% power ([R version 4.3.3; `pwr.t.test`]; Cohen, 1992; Choi & Rush, 2012; Kang, 2021; Plichta & Kelvin, 2013).

5.7.2. Statistical Analysis Plan

Efficacy Analyses

All continuous variables will be summarized using the following descriptive statistics: n (non-missing sample size), mean, standard deviation, median, maximum and minimum. Discrete data will be summarized using n (non-missing sample size), median, minimum,

maximum, and interquartile range or semi-interquartile range. The frequency and percentages (based on the non-missing sample size) of observed levels will be reported for all categorical measures. All summary tables will be annotated with the total population size relevant to that table/timepoint, including any missing observations. Note that sample sizes for individual variables may be different than for the complete case analyses as data in the summary tables may/ may not be present as compared to the complete case dataset.

Primary Efficacy Analysis

Primary outcome(s):

- 1) To determine the efficacy of DSME in the adult Hispanic male population on healthy eating.
 - Hypothesis: N/A
 - Variable: Eating questions (numeric: number of days)
 - Measurement: average number of days
 - Summary data: Mean and SD or median and min/max/SIQR will be calculated for numeric data, as appropriate. Results will be presented in a table, stratified by time.
 - Preliminary Model(s): Data will be modeled using linear regression, generating betas and 95% confidence intervals (PMID: 34325755). Variables included in the model will be the average number of days regressed on time (pre- and post-educational intervention). Results will be presented in a table. Models will be run as two-sided with significance levels set at 0.05. Assumptions for the model will be tested using visualizations, as appropriate.
- 2) To determine the efficacy of DSME in the adult Hispanic male population on staying active.
 - Hypothesis: N/A
 - Variable: Activity questions (numeric: number of days)
 - Measurement: average number of days
 - Summary data: Mean and SD or median and min/max/SIQR will be calculated for numeric data, as appropriate. Results will be presented in a table, stratified by time.
 - Preliminary Model(s): Data will be modeled using linear regression, generating betas and 95% confidence intervals (PMID: 34325755). Variables included in the model will be the average number of days regressed on time (pre- and post-educational intervention). Results will be presented in a table. Models will be run as two-sided with significance levels set at 0.05. Assumptions for the model will be tested using visualizations, as appropriate.
- 3) To determine the efficacy of DSME in the adult Hispanic male population on medication compliance.
 - Hypothesis: N/A
 - Variable: Medication questions (numeric: number of days)
 - Measurement: Total number of days
 - Summary data: Mean and SD or median and min/max/SIQR will be calculated

for numeric data, as appropriate. Results will be presented in a table, stratified by time.

- Preliminary Model(s): Data will be modeled using linear regression, generating betas and 95% confidence intervals (PMID: 34325755). Variables included in the model will be the number of days regressed on time (pre- and post-educational intervention). Results will be presented in a table. Models will be run as two-sided with significance levels set at 0.05. Assumptions for the model will be tested using visualizations, as appropriate.

6 - Trial Administration

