3.2. Hypotheses

Research Hypotheses for the proposed study are as follows:

H₁ – Five weeks of culturally tailored diabetes education will have a statistically significant effect on **diet scores** of adult Hispanic males with T2DM post-intervention.

H₂ – Five weeks of culturally tailored diabetes education will have a statistically significant effect on **exercise scores** of adult Hispanic males with T2DM post-intervention.

H₃ – Five weeks of culturally tailored diabetes education will have a statistically significant effect on **medication scores** of adult Hispanic males with T2DM post-intervention.

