3.8. Exploratory outcome variable(s)

N/A

Exploratory outcome measure 1

N/A

4 - Study Design**4.1 General Design**

A one-group, pretest-posttest, quasi-experimental design (Gray et al., 2017) will be used for this study. This quantitative interventional design was chosen because the study will not have a control group and there will be no random assignment or random selection of participants. However, the independent variable of C-DSME will be manipulated and the outcome variable of DSM behaviors will be measured before and after the intervention for comparison (Gray et al., 2017). Participation in the research study is a requirement to participate in the educational sessions.

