6.5.8 Data Quality Assurance

For the proposed study, potential threats to study validity, and measures to control them, are as follows:

- *A priori* power analysis was completed to guide sample size determination (Cohen, 1992). This was done to control for the potential threat to statistical conclusion validity that can occur due to low statistical power, often associated with inadequate sample size selection. Adequate sample size gives a study adequate power to detect true differences that exist between groups, thereby reducing the threat to statistical conclusion validity (Cohen, 1992).
- The SDSCA-Sp, the instrument of choice for the proposed study, is reliable and valid, thereby minimizing the threat to statistical conclusion validity (Goodman et al., 2020).
- The nonrandomized, one-group, pretest-posttest quasi-experimental design lacks a control group and randomization, which can pose a threat to internal validity of the study (Goodman et al., 2020). The pretest-posttest feature, which allows the sample to be their own control, can potentially minimize this potential threat (Flannelly et al., 2018).

- The proposed target population, as well as inclusion/exclusion criteria for sample selection, have been clearly outlined to potentially minimize threats to external validity.

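### The primary aims and hypotheses claim efficacy, but one uncontrolled pre-post group can only show within-participant change, and self-pairing does not cure that

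*Combined protocol and SAP*

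**What the plan says.** Section 4.1 (General Design) describes "A one-group, pretest-posttest, quasi-experimental design" and states that "the study will not have a control group and there will be no random assignment or random selection of participants".

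Section 5.7.2, under the heading Primary Efficacy Analysis, gives the first aim as "To determine the efficacy of DSME in the adult Hispanic male population on healthy eating". Aims 2 and 3 repeat the formula for staying active and for medication. Each outcome is regressed on time (pre, post) and on nothing else, two-sided at 0.05. In section 3.2, each of H1 to H3 begins "Five weeks of culturally tailored diabetes education will have a statistically significant effect on", followed by the relevant score. Section 5.3 times the survey "at the beginning of Week 1 (pre-intervention) and again at the end of Week 5 (post-intervention) for comparison".

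On validity, section 5.3 (Methodological Rigor) says the design "lacks a control group and randomization, which can pose a threat to internal validity of the study". It continues: "The pretest-posttest feature, which allows the sample to be their own control, can minimize this potential threat". It adds uniform delivery of the intervention as a further safeguard. Section 6.5.8 repeats the self-control point in softer form, saying the pre-post feature "allows the sample to be their own control, can potentially minimize this potential threat".

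**The concern.** Efficacy is a causal claim: scores changed because of the education. A before-after difference in one group estimates total change. Comparing people with themselves removes characteristics that stay fixed over the interval. It leaves in place outside events, the effect of answering the same questionnaire twice, and changes in how people report their own behaviour. Uniform delivery does not remove these either.

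Reporting change is plausible here. The outcomes are self-reported days per week (section 3.4). The second survey follows the last class. The investigator who teaches the classes also helps with survey completion as needed (section 4.4).

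The conclusion is what is at stake. Section 6.5.6 plans publication to inform care of this population, and section 6.5.9 plans registry posting. Nothing in the plan confines the reported result to change over time. The only commitment to discuss limitations, in section 4.3, concerns withdrawals.

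**Working it through.** **1. The plan's own figure.** Inputs from section 5.7.1: standardised effect 0.41, two-sided alpha 0.05, power 0.80, paired test. With the exact noncentral t (noncentrality 0.41 × √n, n − 1 df), power is 0.794 at n = 48 and 0.803 at n = 49. So n = 49 reproduces, and 49 / (1 − 0.50) = 98. The sample-size arithmetic is correct.

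**2. What the time coefficient estimates.** Let τ be the education effect and δ the mean change that would have occurred without it. With one measurement before and one after, and everyone treated,

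E(post − pre) = τ + δ.

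There is one observed contrast and two unknowns. Pairing changes the variance of this contrast but not its expectation. No comparison group, repeated baseline or sensitivity analysis for δ is planned.

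**3. Illustration in a paired test.** Set τ = 0 and express δ in SD units of the paired change. The documents give no drift size, so the values below are assumptions. Noncentrality is δ × √n; for n = 49 this is 7δ, that is 0.7, 1.4 and 2.1 for the three drift sizes. Chance of p<0.05 for one outcome:

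| Drift (SD of change) | 49 pairs | 98 pairs (no attrition) |
|---|---|---|
| 0 | 5.0% | 5.0% |
| 0.1 | 10.5% | 16.5% |
| 0.2 | 27.9% | 50.0% |
| 0.3 | 53.9% | 83.7% |

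The observed mean change that just reaches p = 0.05 is t(0.975, n − 1)/√n, which is 0.29 SD for n = 49 and 0.20 SD for n = 98. A larger sample does not help: it makes a given drift more likely to be significant.

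**4. The same illustration if the regression ignores pairing.** Section 5.7.1 powers a paired test, but the model in 5.7.2 names no term for pairing. Let σ be the SD of a score and ρ the pre-post correlation. The mean difference has true variance 2σ²(1 − ρ)/n, while an unpaired model uses 2σ²/n. The test statistic is then approximately normal with mean δ√(n(1 − ρ)) and variance 1 − ρ, compared with the t critical value on 2n − 2 df. For n = 49 and δ = 0.3, the chance of p<0.05 is 55% at ρ = 0, 39% at ρ = 0.3 and 24% at ρ = 0.5. The correlations are also assumptions. The significance rate falls as ρ rises, but the coefficient still estimates τ + δ and so contains all of the drift.

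**The case against.** The strongest reply is that nothing is hidden. The protocol calls the design quasi-experimental, says there is no control or randomisation, and names the threat to internal validity. The self-control sentences are hedged, and section 5.7.1 describes the target as a difference between the pre and post surveys. All of that stands. It narrows the point to the efficacy and effect wording and the remedy offered. Hedging does not rescue a remedy whose mechanism does not reach time-related change.

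Four stronger readings are tempting and are not supported:

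- *The SAP itself says that self-control solves the problem.* It does not. The statements are in sections 5.3 and 6.5.8, and both are qualified.
- *Any drift will be declared an effect.* The point estimate does absorb any drift. Significance depends on its size and on how the model is fitted, and downward drift could mask a real benefit. No rule in the plan turns p<0.05 into a causal conclusion; H1 to H3 come closest.
- *Regression to the mean must inflate the result.* No eligibility criterion selects on an SDSCA-Sp score or a laboratory value, so this is conjecture.
- *An extra SDSCA-Sp at consent would supply an untreated comparison interval.* The time from consent to Week 1 is not stated, the seven-day recall windows could overlap, and section 3.4 allows 45 to 60 minutes per completion. The documents do not show that such an interval would be informative.

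**Conclusion.** The concern holds as a mismatch between the stated aims and hypotheses and what the design can estimate, together with a mitigation claim that does not do what is said of it. The coefficient combines the education effect with all other change over roughly four weeks, whatever its size. That conclusion needs no numerical assumption.

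The rates of about 11%, 28% and 54% need three: no education effect, 49 pairs analysed by a paired test, and drift of 0.1, 0.2 or 0.3 SD of change. They are illustrations and do not predict this trial. Unpaired analysis lowers them when pre and post scores correlate positively.

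A reader might infer that the study is invalid, under-sized or in need of a control arm. The documents do not support that: the sample size reproduces, and a one-group study can estimate change. The point should be corrected because it alters what the trial may conclude.

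**What to change.** 1. In sections 3.2, 3.3 and 5.7.2 (and the matching objective in the Summary), replace efficacy and effect with change. For example: *to estimate the mean within-participant change in self-reported SDSCA-Sp diet score from Week 1 to Week 5 among participants who complete both surveys*, and likewise for exercise and medication. Retitle the efficacy headings in 5.7.2 to match.
2. In sections 5.3 and 6.5.8, delete the self-control claim or correct it to say that pairing removes stable differences between people and does not address outside events, repeat testing or changes in self-reporting. Do not offer uniform delivery as a control for these.
3. State in 5.7.2 that the observed change cannot be attributed to the education alone, and carry that sentence into the planned reports.

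The cost is wording plus the IRB-approved modification that section 6.2 requires. No data collection, participant time or analysis is added, and the sample size stays at 49 evaluable and 98 enrolled.

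### As written, the primary regression of days on time ignores the pairing of each participant's two scores, although the sample size assumes a paired test

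*Combined protocol and SAP*

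**What the plan says.** Section 5.7.1 takes its effect size from an earlier study: "Based on published SDSCA data for diet and a calculated effect size of 0.41". It then states that with "an alpha of 0.05 and power of 0.80 for a paired two-sided test, a sample size of 49 is adequate", and doubles this to 98 enrolled for a 50% incompleteness rate.

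Section 5.7.2 gives one model per primary outcome: "Data will be modeled using linear regression, generating betas and 95% confidence intervals". For diet and exercise the terms are: "Variables included in the model will be the average number of days regressed on time (pre- and post-educational intervention". For medication: "Variables included in the model will be the number of days regressed on time (pre- and post-educational intervention". Testing is specified as follows: "Models will be run as two-sided with significance levels set at 0.05". The models are labelled preliminary, but they stand under the primary efficacy heading and no other model is given.

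Under methodological rigor, section 5.3 relies on the repeated measurement of the same people: "The pretest-posttest feature, which allows the sample to be their own control, can minimize this potential threat". Section 6.4 gives each participant one study ID throughout, so the two surveys can be linked.

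**The concern.** Stacking the pre and post scores and regressing them on a two-level time variable is algebraically the equal-variance two-sample t-test. That test assumes independent rows, but here each completer supplies two. If the two scores are positively correlated, the independent-rows standard error includes between-person variation that cancels when each person is compared with himself. The own-control feature that section 5.3 relies on is then lost from the analysis.

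At stake are the confidence interval and p-value for all three primary outcomes, and the stated power for diet. Section 5.7.2 plans to check assumptions with plots but does not say that any plot will examine within-person dependence.

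**Working it through.** **Inputs.** From 5.7.1: effect size 0.41 (diet), two-sided alpha 0.05, power 0.80, paired test, 49 completers, 50% incompleteness. From 5.7.2: time as the only term, two-sided 0.05. Not in the documents: the pre-post correlation rho (assumed 0.1 to 0.7) and the standard deviation by which 0.41 was scaled.

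**1. Reproduce the plan's figure.** Read 0.41 as mean change divided by the SD of change. The paired t-test has n - 1 degrees of freedom and noncentrality 0.41 × sqrt(n).
- n = 48: power 0.794
- n = 49: power 0.803

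So 49 is the smallest adequate number of pairs, and 49 / (1 - 0.5) = 98. The plan's figures reproduce, which supports this reading of 0.41.

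**2. Compare standard errors.** Let s be the SD of a score at either time and n the number of pairs.
- Paired: SE = s × sqrt(2(1 - rho)/n)
- Regression on time: SE is about s × sqrt(2/n)
- Ratio: 1/sqrt(1 - rho)

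Both analyses give the same point estimate, the difference between the two means.

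**3. Power of the regression at 49 pairs.** Its t statistic is about sqrt(1 - rho) times the paired statistic, and the critical value with 96 degrees of freedom is 1.985. With 0.41 × sqrt(49) = 2.87,

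power is about P(Z > 1.985/sqrt(1 - rho) - 2.87).

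At rho = 0.5: 1.985 × 1.414 = 2.807, and P(Z > -0.063) = 0.525. Simulation of bivariate-normal pairs gives 0.53. The simulated results, with the number of pairs needed for 80% power from the same approximation, are:

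| rho | CI too wide by | Type I error (nominal 5%) | Power, 49 pairs | Pairs for 80% |
|---|---|---|---|---|
| 0 | 1.00 | 5% | 81% | 48 |
| 0.1 | 1.05 | about 4% | 78% | 52 |
| 0.3 | 1.20 | about 2% | 69% | 62 |
| 0.5 | 1.41 | about 0.6% | 53% | 79 |
| 0.7 | 1.83 | about 0.05% | 24% | 118 |

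Repeat simulations differ by up to about one percentage point in power. Under the paired test, power stays at about 80% in every row.

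**4. Alternative scaling of 0.41.** If 0.41 is a fraction of the raw-score SD, the regression at 49 pairs has about 52% to 54% power over rho 0.1 to 0.7, almost regardless of rho. The two-sample formula gives 0.52, and about 95 complete pairs would be needed for 80%.

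**The case against.** The strongest reply is that the plan may be under-specified rather than committed to an unpaired analysis. It never says the rows are independent, calls the models preliminary, and cites a methods paper that cannot be checked here. The sample size, the own-control argument and the single ID all treat the data as paired. An analyst might therefore pair the scores anyway. That is fair as to intent, but the plan lists the variables in each model and no participant term is among them. The wording needs to change in either case.

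Three further limits stand:
- The loss depends on rho. At zero there is none, and at a negative rho the direction reverses (type I error about 7% at -0.2). A positive value is expected for the same people on the same instrument, but that is an expectation and not a figure in the plan.
- The figures are for 49 completers, the plan's own 50% case. More completers would recover some power: 79 would restore 80% at rho 0.5. At rho 0.7 even all 98 would fall short of the 118 needed.
- For positive rho the error is conservative, so false positive findings become rarer.

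A reader might infer that a real change of the planned size will probably be missed. The numbers do not support that in general: power falls below one half only when rho exceeds about 0.52. A reader might also take the 0.84 test-retest reliability quoted in section 5.5 as the pre-post correlation, which would give almost no power. That figure describes the instrument's stability and is not a correlation across a five-week behavioural intervention, so no result here uses it.

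**Conclusion.** The analysis is wrong as written. The primary model omits the pairing on which section 5.7.1 depends, and this applies to all three primary outcomes. For positive rho the estimated change is correct, the interval is 1.05 to 1.83 times too wide over rho 0.1 to 0.7, and the test is conservative.

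The power statement is narrower. It covers diet only, because the documents state no power for exercise or medication. It also rests on 49 completers, an assumed rho, and 0.41 being mean change over SD of change. On that basis, power is about 78% to 24% over the same range instead of 80%.

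A reader might infer that the sample size is mistaken or that the trial cannot reach 80% power. Neither follows. The 49 and 98 are correct for the paired test, and an analysis that keeps the pairing restores the stated power.

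**What to change.** In section 5.7.2, for each of the three outcomes, replace the regression on time with an analysis that keeps the pairing. The direct match to 5.7.1 is a paired t-test or an intercept-only model of the change score, on participants with both surveys scored. A linear mixed model with a fixed effect of time and a random intercept for study ID is equivalent on complete pairs, provided the estimated participant variance is above zero and the degrees of freedom match. Report the mean within-person change with its 95% confidence interval.

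In section 5.7.1, state which standard deviation scales 0.41.

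The cost is about one sentence per outcome and a line of code. The study ID already links the surveys, so no new data are needed and the target of 98 is unchanged.
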